### Details of PET Study

Given that it is very difficult to acquire meaningful functional MRI scans with DBS electrodes in the brain, we have decided to acquire functional PET scans to study how DBS changes the speech neural networks in our patients while they talk. In collaboration with UBC [name], a world-leader in PET imaging, we

have decided to investigate the feasibility of applying a very innovative and informative approach to acquiring FDG-PET scans developed by a group from Harvard. The technique is called “fPET-FDG”. Briefly, this involves the participant being intravenously administered with fluorodeoxyglucose (FDG) in saline solution at a constant infusion rate of 0.01 ml/s for 90 mins (duration of a single scan). Venous blood samples will then be collected every 10 min from the other arm during scanning, centrifuged to obtain plasma, and aliquoted in a gamma count that had been calibrated to the PET scanner to measure venous activity during the experiment. This methodology follows the recent publication by the Harvard group which can be found in reference 10 for details.

Ultimately, this methodology overcomes technical limitations in traditional PET methodology (Bolus Method) which involves two scans and two large doses of FDG injection at the start of the experiment. The only caveat is that we will also have to acquire venous blood samples throughout the experiment in this new method. Together with consulting with [name] and her team, we believe that fPET-FDG is most effective approach in answering our scientific question given that we are trying to dynamically measure glucose metabolism during a task and trying to acquire brain scans that closely parallel functional MRI scans.

\*Pilot Test of Scan- Before implementing this methodology into the overall trial, we will pilot this in a healthy control and our most severe trial participant. (Note- Both of them already been recruited as the patient part of the trial has asked a friend to be a healthy control for this scan). The purpose of the pilot testing is to optimize acquisition parameters, optimize the behavioral task, and determine if we will observe meaningful changes using this new fPET-FDG methodology.

\*Scans for The Trial- If the pilot testing is successful, we will implement this new fPET-FDG methodology into our overall trial. Patients will first have a Raclopride-PET Scan to study how dopamine is modulated in their brains with DBS-ON and DBS-OFF. They will then have this new fPET-FDG scan optimized in the pilot testing. Both of these scans will take place at the 3, and 6 month mark of the study (see trial figure for clarification)

### **Adverse Events**

There can be temporary side effects related to the stimulation spreading outside the target area of the brain. These side effects depend on what area of the brain is being stimulated and can include tingling, muscle tightness, double vision, hoarse speech, and dyskinesia. These temporary side effects can be adjusted and resolved by the DBS Clinicians and be minimized. In this study, if any adverse events occur, the patient will be able to contact [name] on a 24/7 basis. The DTI scan is a standard MRI scan and carries no additional risk to the patient. The PET scan will use ligands that expose the patient to radiation. Each PET scan entails a radiation exposure similar to a single transatlantic 6-hour flight.

### **Significance**

The significance of this research is two-fold: improving the patients’ spasmodic dysphonia symptoms and secondly, providing neurosurgeons with a strategy of treating spasmodic dysphonia. This trial will be of international significance as it is the first time these dystonia patients will be undergoing DBS intervention.

In the past, otolaryngologists have been involved in treating spasmodic dysphonia cases. Our study has the potential to show that perhaps, DBS can be used for pure spasmodic dysphonia as well. This will be the largest study reported in the literature on studying the effects of DBS on spasmodic dysphonia. Based on the limitations of existing treatments, DBS can provide SD patients with a long-term and sustained relief from their voice disorder. Our work has the potential to revolutionize the care provided for these patients.

SD is the third most common focal dystonia followed by cervical dystonia and blepharospasm. This disorder has classically been thought of as a disorder of the laryngeal muscles or of psychogenic origins. Recent neuroimaging studies have emerged indicating the presence of a central neurological abnormality in the basal ganglia of SD patients (6). Thus, our current investigations are aimed at determining the efficacy of DBS for SD.

***Un-randomization:***

In the case of an adverse or unanticipated event during this surgical trial, the patients will be un-randomized completely turned off. However, based on the literature and our 15-year experience, we expect all patients to experience at least some benefit (even if minimal to none) rather than deteriorating.

**Novelty**

DBS therapy has been used in clinical practice for the last 15 years. Recent “indications” for DBS include Alzheimer’s disease, anorexia nervosa, and even obesity. Unlike these disorders, LD is a movement disorder that can follow track of DBS for Parkinson’s disease, essential tremor, and primary dystonia as the surgical gold-standard treatment. We hope to provide a novel neurosurgical treatment for LD and potentially show this is a new “indication”. While existing treatments such as BTX therapy and laryngeal nerve surgery aim to treat SD at the neuromuscular level, our goal is to use DBS to treat the central neurological abnormality that precipitates this voice disorder.

**Statistics**

We will compare the primary (Unified Spasmodic Dysphonia Rating Scale) and secondary endpoints (Quality of Life) at baseline, for the off- stimulation period and the on-stimulation period, with repeated measures ANOVA. For the endpoints in which a significant effect of timepoint ( $p < 0.05$ ) was identified, pairwise comparisons will be performed between each of the three timepoints (baseline *versus* off stimulation, baseline *versus* on stimulation, and on stimulation *versus* off stimulation) and a Bonferroni-corrected p values will be completed.

We will also compare the effect of randomisation sequence on the difference in USDRS scores between the on-stimulation and off-stimulation periods in the blinded phase of the trial using an unpaired *t* test.

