### Study Design

To investigate our hypothesis, we will conduct a prospective, randomized, double-blinded, crossover Phase 1 DBS trial in LD patients. Patients will be randomized to either active or sham-stimulation for 3 months, crossed-over, and conclude with open-label treatment for 6 months. Patient and assessors will be blinded to treatment allocation. Below is a graphical illustration of trial.

Previous Phase 1 trials for new indications of DBS have recruited N=6 patients. We plan to also recruit N=6 patients for this trial from the Pacific Voice Clinic. We will use a computer-generated 1:1 pairwised randomization sequence when the patients are enrolled into the trial, so that similar numbers of patients are recruited to each study group. Patients will be evaluated in a double-blinded manner for their voice and voice-related quality of life. Patients and rating clinicians will be masked to treatment allocation; an unmasked clinician will be responsible for programming the stimulation.

DBS stimulation parameters will be chosen based on standard programming guidelines. Primary endpoints will assess: (1) patient improvement in SD using the Unified Spasmodic Dysphonia Rating Scale (2) assess patient quality of life using the Voice-Related Quality of Life. Patients will also be asked their subjective assessment of each of the settings. [name] will be administering these scales.

We also will acquire two advanced neuroimaging scans: PET and DTI. The former will allow us to monitor neural network wide changes as a result of DBS. DTI will allow us to determine which white matter tracts are being activated as a result of this surgery. Once pilot\* testing of the PET protocol is completed, patients enrolled in this trial will be asked to obtain a PET scan at end of the 3-month mark and at the 6-month mark (see trial timeline above). DTI scan will only be required pre-operatively. The neuroimaging arm of our surgical trial will add considerable scientific rigour to our trial and helps us further elucidating the neurobiology of this disease.

At the Vancouver General Hospital (VGH), we have a 17-year experience with Deep Brain Stimulation Surgery. As of 2012, we have performed over 400 of these operations including DBS stimulator programming.

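### The on-versus-off comparison is made only after a significant omnibus F test, and no effect estimate or confidence interval is planned for any contrast

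*Combined protocol and SAP*

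**What the plan says.** The Study Design section describes a "prospective, randomized, double-blinded, crossover Phase 1 DBS trial in LD patients": active and sham stimulation for three months each in randomized order, then six months open label. The sample size rests on precedent ("Previous Phase 1 trials for new indications of DBS have recruited N=6 patients"; "We plan to also recruit N=6 patients for this trial"). No effect size, SD, power or precision target is given.

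The Statistics section sets out three steps:

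- Baseline, off and on are compared by repeated measures ANOVA for the Unified Spasmodic Dysphonia Rating Scale (USDRS) and for quality of life.
- The follow-up is restricted to endpoints that pass: "For the endpoints in which a significant effect of timepoint" is found at p < 0.05. For those, "pairwise comparisons will be performed between each of the three timepoints", with Bonferroni-corrected p values.
- Separately, and without any condition on the F test, an unpaired t test compares the on-off USDRS difference between the two randomization sequences.

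No estimate, standard error or confidence interval is mentioned for any contrast.

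**The concern.** On versus off is the only comparison protected by randomization and blinding. Under the written rule it is made only if a three-level test passes, and one of those levels, baseline, is not a randomized condition. Whether the randomized contrast is examined therefore depends partly on how baseline differs from the other two.

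The F-test condition is not needed to control error, because Bonferroni correction over the three comparisons already does that.

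The most useful product of a first six-patient trial is an effect size with its uncertainty, since a later trial would be planned on it. The plan does not commit to producing one. If the F test fails, no on-off result is planned. If it passes, a p value is planned, and any estimate then added has been through a significance filter. What is reported would be left to a choice made after the results are known.

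**Working it through.** **Plan's own figure.** There is nothing to reproduce: N = 6 comes from precedent, with no calculation behind it.

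**Inputs from the documents.** n = 6 and 1:1 allocation (Study Design); three conditions, F test at 0.05, three pairwise comparisons (Statistics).

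**Assumptions.** Scores are normal, all paired differences have equal variance, there is no period or carryover effect, and nobody drops out. Let d be the true on-off benefit in SDs of a paired difference. The documents do not give d, so it is varied. Two cases are taken for baseline: equal to off, and worse than off by d/2.

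**Chance that the comparison is made.** The F test has 3 − 1 = 2 and 2 × 5 = 10 df, with critical value 4.10. With the SD of a paired difference set to 1, the within-patient error variance is 1/2. The noncentrality is λ = n × Σ(μⱼ − μ̄)² / (1/2).

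- Baseline equal to off: the sum of squares is (2/3)d², so λ = 6 × (2/3)d² × 2 = 8d².
- Baseline worse by d/2: the means are d/2, 0 and −d, the sum of squares is (7/6)d², so λ = 6 × (7/6)d² × 2 = 14d².

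The noncentral F distribution then gives the probability of passing. The mean on-off estimate among trials that pass comes from 400,000 simulated trials per scenario, and the simulated pass rates agree with the formula.

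| d | Baseline | λ | F test passes | Comparison not made | Mean estimate ÷ truth, given a pass |
|---|---|---|---|---|---|
| 0.5 | = off | 2.0 | 18% | 82% | 1.8 |
| 0.8 | = off | 5.12 | 40% | 60% | 1.3 |
| 1.0 | = off | 8.0 | 58% | 42% | 1.2 |
| 1.5 | = off | 18.0 | 91% | 9% | 1.04 |
| 0.5 | worse by d/2 | 3.5 | 28% | 72% | 1.5 |
| 1.0 | worse by d/2 | 14.0 | 82% | 18% | 1.07 |
| 1.5 | worse by d/2 | 31.5 | 99% | 1% | 1.00 |

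A 95% interval shown only after a pass covers the truth in 85% of such trials at d = 0.5 with baseline equal to off. Shown always, it covers 95% at every d tried.

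**Precision if always reported.** In SDs of the paired difference:

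- Simple paired interval: t(5, 0.975)/√6 = 2.571/2.449 = 1.05.
- Adjusted for period, with three patients per sequence: the estimate is the average of the two sequence means of the on-off difference. Its standard error is (s/2)√(1/3 + 1/3) = s/√6 on 4 df, so the half-width is 2.776/2.449 = 1.13.

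**The case against.** Four points can fairly be made for the plan.

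1. *It is silent on estimates; it does not forbid them.* The condition applies to significance tests, and descriptive means could still be published. This stands. A reader might infer that the trial will report either no effect size or an exaggerated one. The text does not support that. If only p values are output, there is no effect size to exaggerate; exaggeration arises only if estimates are published because the F test passed. Nor does any section say that a non-significant F will be taken as lack of efficacy.

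2. *One analysis escapes the condition.* The sequence t test needs every patient's on-off USDRS difference, so for that endpoint the differences are computed regardless. This stands, but the test asks whether the two sequences differ. It neither estimates nor tests the on-off effect, and it does not cover quality of life.

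3. *The size depends on unstated values.* This also stands. If baseline is worse than off, the F test passes more often and the inflation shrinks. At d of 1.5 or more, inflation from the F-test condition is 4% or less in either case. The investigators evidently hope for a large effect, although that hope is not evidence about d.

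4. *The trial is labelled Phase 1.* The Significance section does say "our current investigations are aimed at determining the efficacy of DBS for SD", and a reader might infer that six patients are to deliver a formal efficacy verdict. That sentence is background narrative, the surrounding text is tentative, and no efficacy decision rule exists. Rewording it would be a preference, not a correction.

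**Conclusion.** The point holds in a limited form. As written, the randomized contrast is examined only after a significant omnibus test that includes the non-randomized baseline, and no contrast has a planned estimate or interval. That follows from the text and needs no assumption.

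The size does rest on assumptions. For true effects between 0.5 and 1.0 SD, the planned comparison would be missing in 42% to 82% of trials if baseline equals off. At d = 0.5 and 1.0 the figures are 72% and 18% if baseline is worse by half the effect. Inflation of an estimate shown only after a pass runs from about 1.8 down to 1.07 over the same range and is negligible at 1.5 SD or more. It is a possible consequence of selective publication, not something the plan commits to. This is a worthwhile and cheap improvement, not a flaw that invalidates the trial.

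**What to change.** In the Statistics section, replace the conditional sentence with wording such as:

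*For USDRS and V-RQOL, the on-minus-off mean difference with its 95% confidence interval, adjusted for period, will be reported whatever the result of the F test. The comparisons with baseline will be reported as secondary, also with intervals.*

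The period adjustment suits a two-period crossover and, for USDRS, uses the same sequence means and within-sequence SD that the planned t test already requires. A listing of individual differences is best left out, because the Organization section undertakes that publications will not refer to individual patients.

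The change needs no new data, patients or procedures. Its price is candour. With a half-width of about 1.13 SD after period adjustment (1.05 without), the result will read as a first estimate and not as a verdict on efficacy.

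### On versus off stimulation, the only contrast that the design randomises and masks, is not named as primary and is Bonferroni-corrected alongside two before-after contrasts, at a cost in power that depends on an unstated error term

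*Combined protocol and SAP*

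**What the plan says.** The Study Design section of the combined protocol and SAP sets up a two-period crossover: "Patients will be randomized to either active or sham-stimulation for 3 months, crossed-over". Patients and raters are masked to which period is active. The sample size is set by precedent: "Previous Phase 1 trials for new indications of DBS have recruited N=6 patients", followed by "We plan to also recruit N=6 patients for this trial".

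The Statistics section compares "the primary (Unified Spasmodic Dysphonia Rating Scale) and secondary endpoints (Quality of Life") across three conditions, "at baseline, for the off- stimulation period and the on-stimulation period, with repeated measures ANOVA". If the effect of timepoint has p < 0.05, "pairwise comparisons will be performed between each of the three timepoints": baseline versus off, baseline versus on, and on versus off. The p values are Bonferroni-corrected. The divisor is not given; 3 is the natural reading. The section does not say which of the three contrasts decides the trial, nor whether each pairwise test uses its own paired differences or the pooled ANOVA error.

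A further unpaired t test asks whether randomisation sequence affects the on-off USDRS difference. It tests the influence of order, not whether on differs from off.

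The Study Design section, unlike the Statistics section, lists two primary endpoints: "Primary endpoints will assess: (1) patient improvement in SD using the Unified Spasmodic Dysphonia Rating Scale" and "2) assess patient quality of life using the Voice-Related Quality of Life".

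**The concern.** Randomised order and masking protect on versus off and nothing else. Baseline always comes first and lies outside both, so the two baseline contrasts mix stimulation with surgery, time and expectation. The plan nevertheless gives the three contrasts equal standing and divides the alpha among them. With six patients, the contrast that isolates stimulation is tested at about 0.017 rather than 0.05, to make room for two that cannot isolate it.

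Because no contrast is named as the deciding one, the plan also leaves open what a mixed result would mean, for example baseline versus on significant and on versus off not.

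**Working it through.** The documents state no power, SD, effect size or sidedness, so there is no figure of the plan's own to reproduce.

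**Inputs from the plan.** n = 6 (Study Design). Three conditions, an ANOVA gate at 0.05, and three Bonferroni-corrected pairs (Statistics). Inferred divisor 3: 0.05/3 = 0.0167 per contrast.

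**Assumptions.** Two-sided tests, normal errors, no missing data, equal variances and correlations across conditions, and baseline mean equal to off mean unless stated. The effect d is the mean on-off difference divided by the SD of that difference, taken from 1.0 to 2.0.

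**Formula.** Power is the probability that a noncentral t variable with noncentrality d × √6 exceeds the critical value in absolute size. For d = 1.435 the noncentrality is 1.435 × 2.449 = 3.51. The degrees of freedom depend on the error term:

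| Error term | df | Critical t at 0.05 | Critical t at 0.05/3 |
|---|---|---|---|
| Paired differences | 5 | 2.571 | 3.534 |
| Pooled ANOVA error | 10 | 2.228 | 2.870 |
| Period-adjusted (mean of the two sequence-specific on-off differences, 3:3 split) | 4 | 2.776 | 3.961 |

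The full two-step rule, F(2,10) > 4.103 followed by the corrected pairwise test, was simulated with 400,000 trials per scenario.

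**Like for like: power for on versus off, single test at 0.05 against the plan (gate plus 0.05/3).**

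| d | Paired, 0.05 | Paired, plan | Pooled, 0.05 | Pooled, plan |
|---|---|---|---|---|
| 1.0 | 51% | 25% | 60% | 39% |
| 1.435 | 80.0% | 54.3% | 88.5% | 72.9% |
| 2.0 | 97% | 85% | 99% | 96% |

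At d = 1.435 the loss is 80.0 − 54.3 = 25.7 points (paired) or 88.5 − 72.9 = 15.6 points (pooled). The effect detectable with 80% power rises from 1.43 to 1.88 SD (paired) or from 1.27 to 1.55 SD (pooled).

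**How much is due to the gate.** With paired tests at d = 1.435, Bonferroni alone gives 55.0%. Adding the gate gives 54.3%, or 53.1% if the baseline mean lies midway between off and on, so the gate costs 0.7 or 1.9 points. With pooled error it costs nothing: 2.870² / 2 = 4.12 exceeds 4.103, so a pair significant at 0.05/3 already implies a significant F. The gate would matter more if Bonferroni alone were dropped: the paired 0.05 test at d = 1.435 would then fall from 80% to 77% (baseline equal to off) or 73% (midway).

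**If the plan meant pooled error.** The comparison is then between the plan as it stands and the test that would replace it:

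| d | Plan, pooled | Paired t at 0.05 | Gain | Period-adjusted at 0.05 | Gain |
|---|---|---|---|---|---|
| 1.0 | 38.6% | 50.7% | +12.1 | 46.3% | +7.7 |
| 1.435 | 72.9% | 80.0% | +7.1 | 74.8% | +1.9 |
| 2.0 | 96.1% | 97.1% | +1.0 | 94.8% | −1.3 |

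**Type I error.** When all three means are equal, the planned rule declares on versus off significant in about 1.0% of trials (paired) or 1.7% (pooled), both below 5%.

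**The case against.** The strongest reply is that the plan contains no error here. It prespecifies a valid, conservative procedure that includes on versus off, in a Phase 1 study of six patients with no power target. Any loss of power is measured against a standard that the documents never set. This stands, and it makes the point an inexpensive improvement rather than a correction.

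Second, the 26-point loss assumes separate paired tests. An ANOVA followed by pairwise comparisons could equally use pooled error, and the net gain from a paired 0.05 test is then about 12, 7 and 1 points at 1.0, 1.435 and 2.0 SD. Against the period-adjusted test the gain is small and turns slightly negative from about 1.75 SD. This also stands: the documents do not settle where in this range the benefit lies.

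Third, a reader might infer that the omnibus gate is a main source of the loss. The figures do not support that.

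Fourth, a reader might fear that a significant baseline-versus-on result would be taken as proof of stimulation. The plan does not say that it would be. Its three-way set often exposes a before-after shift: with a pure shift of 1.435 SD, baseline versus off is also significant in 66.5% (paired) or 84.6% (pooled) of the trials where baseline versus on is significant and on versus off is not.

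Finally, the sequence test shows that the authors recognise the on-off difference as a key quantity. It still does not make on versus off the deciding test.

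**Conclusion.** The point holds as a matter of efficiency and clarity. The one contrast protected by the design has no priority in the analysis and gives up alpha to two before-after contrasts. Over 1.0 to 2.0 SD the like-for-like loss runs from about 26 points down to 12 with paired tests, and from about 21 down to 3 with pooled error. If pooled error was intended, the realistic gain from the recommended paired test is about 12 points down to 1. All these sizes rest on assumed effects, a divisor of 3 and two-sided tests.

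The documents do not support a claim of inflated false positives or of an invalid analysis, nor do they support 26 points as the established loss. The conflict over quality of life as a primary endpoint is a separate inconsistency; it matters here only because a second primary endpoint could split the 0.05. The change is worth making before analysis, but the trial does not fail without it.

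**What to change.** In the Statistics section, name the within-patient on-minus-off USDRS difference in the blinded crossover phase as the single primary contrast. Test it by a paired t test at two-sided 0.05, not conditional on the omnibus F test, and report the estimate with its 95% confidence interval.

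Give the period-adjusted estimate (4 df) as a sensitivity analysis, and state that it does not decide. The choice has a price in either direction: at 1.435 SD with no period effect, the paired test has 80.0% power against 74.8% for the adjusted test. If a period effect moves each on-off difference by 0.5 SD up or down according to sequence, the paired test drops to 70.8% while the adjusted test stays at 74.8%.

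Report baseline versus off and baseline versus on as secondary estimates with confidence intervals, described as change since before surgery and not as evidence for stimulation. If any pairwise tests are kept, state their error term and the Bonferroni divisor.

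Align the Study Design section with the Statistics section, so that USDRS is the one primary endpoint and the 0.05 is not split.

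The cost is wording in two sections, with no added patients or data. The downside is that the two baseline contrasts lose formal test status.

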**Organization**

At the Surgical Centre for Movement Disorders at Vancouver General Hospital, we have a 15-year experience with DBS surgery and programming for movement disorders. Patients eligible for this study will be all patients who have already underwent or who will be undergoing thalamic DBS surgery to ameliorate their essential tremor. Patients will be tracked through [name] clinic and given a research identification number. After enrollment, they will be followed-up by [name] and programming will begin one-month after surgery. Data will be burned onto a CD using only their research identification number. This data will then be analyzed to determine if there is an improvement in the patient’s spasmodic dysphonia symptoms and quality of life. The results will be published in a peer-reviewed journal with no reference to individual patients.

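### The main crossover analysis has no period term, and the 3 v 3 sequence t test cannot stand in for one

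*Combined protocol and SAP*

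**What the plan says.** Under Study Design, "Patients will be randomized to either active or sham-stimulation for 3 months, crossed-over, and conclude with open-label treatment for 6 months". The sample size is six ("We plan to also recruit N=6 patients for this trial from the Pacific Voice Clinic"), justified by earlier Phase 1 DBS trials and not by a power calculation. On allocation: "We will use a computer-generated 1:1 pairwised randomization sequence when the patients are enrolled into the trial". This implies 3:3 if all six are enrolled and complete, although the section promises only similar numbers per group.

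Under Statistics, the USDRS and quality of life are compared "at baseline, for the off- stimulation period and the on-stimulation period, with repeated measures ANOVA". If the overall test gives p < 0.05, the three pairwise comparisons follow with Bonferroni correction. The factor that the plan calls timepoint is really condition; the model has no term for first or second blinded period.

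The only order-related analysis is the unpaired t test introduced by "We will also compare the effect of randomisation sequence on the difference in USDRS scores between the on-stimulation and off-stimulation periods". It covers the USDRS but not quality of life, and no rule says what follows from its result.

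Two other passages bear on the point. After an adverse or unanticipated event, "the patients will be un-randomized completely turned off" (Un-randomization), and no missing-data rule is given. Under Organization, "programming will begin one-month after surgery".

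**The concern.** In a two-period crossover, on-first patients have stimulation in period 1 and off-first patients have it in period 2. Any shift between the periods therefore moves the on-off difference up in one sequence and down in the other. A model with no period term treats that systematic split as noise. With six patients there is little room for extra noise, and a real on-off difference could be missed.

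Starting programming a month after surgery limits early recovery effects. It does not exclude a later trend across the two 3-month periods, or practice effects.

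The sequence t test may look like a safeguard, but it neither adjusts the estimate nor removes the period variance from the error. A non-significant result on 4 degrees of freedom could be misread as showing that order does not matter.

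**Working it through.** **Inputs from the documents.** N = 6 and 1:1, hence 3:3 if complete; overall test at 0.05; three pairwise comparisons, so 0.05/3 = 0.0167 each; sequence test with 3 + 3 − 2 = 4 df. The plan gives no power figure to reproduce.

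**Assumptions.** The documents give no USDRS SD, so the unit is the SD of the on-off difference. The on-off effect δ is 1.43, the effect that a paired t test in six patients detects with 80% power at two-sided 0.05. The period effect π (period 1 minus period 2) runs from 0 to 1. Tests are two-sided, the baseline mean equals the off mean, and baseline, off and on are equally correlated, so each has residual SD 1/√2.

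**1. Expected on-off difference D.** On-first: δ + π. Off-first: δ − π. At 3:3 the mean is (3(δ + π) + 3(δ − π))/6 = δ, so it is unbiased.

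**2. Error term at 3:3.**
- The expected sample variance of D is 1 + (6/5)π² = 1.00, 1.30 and 2.20 at π = 0, 0.5 and 1.
- In the ANOVA each patient carries +π/2 and −π/2 in the two blinded periods and 0 at baseline. This adds 6 × 2 × (π/2)² = 3π² to the residual sum of squares on 10 df.
- The residual mean square is therefore 0.50 + 0.30π² = 0.50, 0.575 and 0.80. With a period term it stays at 0.50 on 9 df.

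**3. Power for on v off in the full plan** (0.05 gate, then 0.0167 with pooled ANOVA error; 200,000 simulated trials):

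| Period effect (SD) | No period term | With period term |
|---|---|---|
| 0 | 72.5% | 70.6% |
| 0.25 | 70.9% | 70.6% |
| 0.5 | 66.0% | 70.5% |
| 0.75 | 58.7% | 70.6% |
| 1 | 48.5% | 70.5% |

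Break-even is just under 0.3 SD. With no true on-off effect, the plan rejects on v off in 1.6%, 1.2% and 0.4% of trials at π = 0, 0.5 and 1, against 1.6 to 1.7% with the term. The plan's test is conservative, not anti-conservative.

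**4. Stand-alone on-off test** (paired t on 5 df v period-adjusted on 4 df):

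| Period effect (SD) | Alpha 0.05 | Alpha 0.0167 |
|---|---|---|
| 0 | 80 v 75% | 55 v 46% |
| 0.5 | 71 v 75% | 42 v 46% |
| 1 | 45 v 75% | 18 v 46% |

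Break-even is near 0.4 SD.

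**5. One patient lost (3:2).** The unadjusted mean is δ + (3π − 2π)/5 = δ + π/5. The bias is 0.10 SD at π = 0.5 and 0.20 SD at π = 1, with its sign set by which sequence loses the patient. Averaging the two sequence means gives δ, with no bias.

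**6. Sequence t test.**
- With carryover λ from on into the later off period, the on-first mean becomes δ + π − λ. The sequence contrast is 2π − λ, so period and carryover cannot be separated.
- The standard error is √(1/3 + 1/3) = 0.816 SD. The 95% CI half-width is 2.776 × 0.816 = 2.27 SD.
- With no carryover, non-central t power is 16% at a contrast of 1 SD (π = 0.5) and 46% at 2 SD (π = 1). Power of 80% needs a contrast of 3.07 SD.

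**7. What the period term does not do.** The average of the two sequence means is δ − λ/2 with or without the term. At λ = 1 SD both estimates are off by −0.5 SD.

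**The case against.** At 3:3 the planned analysis is valid: no bias and no excess type I error. What remains is an efficiency argument, in a trial with no stated power target, resting on an on-off effect and period effects that the documents do not give. All of this is true.

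The fix can also lose power. The Statistics section does not say that the pairwise comparisons use the pooled ANOVA error. With the same gate and ordinary paired comparisons at 0.0167, power without v with a period term is 54 v 45% with no period effect, 46 v 45% at 0.4 SD, 42 v 45% at 0.5 SD and 18 v 45% at 1 SD. Below about 0.4 SD the term then costs power, by up to 9 points. This stands, and the sponsor should weigh it.

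The 3:2 case is hypothetical, since the Un-randomization section does not say that data would be dropped. Even at 3:2 and π = 0.5, mean squared error is nearly equal: 1/5 + 0.10² = 0.210 unadjusted against (1/4)(1/3 + 1/2) = 0.208 adjusted. A bias in the favourable direction can even raise unadjusted power (59 v 54% in the pooled plan at 0.5 SD), but that power comes from a biased estimate and is no reason to omit the term.

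Absent carryover, the sequence t test is a test of period, so the plan does look at order. Where the power loss is largest the test is also less weak (46% at 1 SD). It still misses more often than not at that size, and detecting a period effect does not adjust for it.

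Finally, baseline always comes first, so a period term helps only on v off; both baseline comparisons stay confounded with time.

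**Conclusion.** The concern holds. At 3:3 the omission costs power and not validity; bias arises only if the sequences become unequal. In the pooled-error plan the loss is about 4 to 5 points at a 0.5 SD period effect and about 22 points at 1 SD. If the comparisons are ordinary paired tests, the term pays only above about 0.4 SD. These sizes rest on the assumed 1.43 SD effect, equal correlations and period effects whose true size is unknown. That the sequence test cannot fill the gap rests on less: its 4 df and its mixing of period with carryover follow from the design. The change is advisable because it is standard for a crossover and uses the same data.

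**What to change.** Add period as a fixed effect to the planned analysis:
- Condition (baseline, off, on) and period as fixed effects, with period coded +1/2 and −1/2 for the two blinded periods and 0 at baseline.
- Patient as a block or random effect.
- The stated 0.05 gate and Bonferroni correction kept, and the error term for the pairwise comparisons named.

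Report the sequence contrast as an estimate with a 95% CI, labelled as period plus carryover. State that its p value will not be taken as evidence that order does not matter, that the period term does not correct for carryover, and that the baseline comparisons remain confounded with time.

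The cost is SAP wording and one degree of freedom. If there is truly no period effect:
- pooled plan (10 to 9 df): power falls from 73 to 71%;
- stand-alone on-off test (5 to 4 df): from 80 to 75% at 0.05, or from 55 to 46% at 0.0167;
- pooled plan after one loss (8 to 7 df): from 59 to 54%.
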